4.3 Exclusion Criteria

Subjects will be ineligible for this study if they meet **any** of the following criteria:

1. Pregnant, planning on becoming pregnant (during treatment and up to 6 months after the EOT), or breast-feeding female subject, or male subject whose female partner is pregnant or planning on becoming pregnant (during treatment and up to 6 months after the EOT)
2. Other than CHC with or without compensated cirrhosis, clinically significant cardiovascular, respiratory, renal, gastrointestinal, hematologic, neurologic, thyroid or any other medical illness or psychiatric disorder, as determined by the Investigator and/or Sponsor's Medical Monitor.
3. History or other clinical evidence of significant or unstable cardiac disease (e.g., angina, congestive heart failure, myocardial infarction, diastolic dysfunction, significant arrhythmia, coronary heart disease, and/or clinically significant ECG abnormalities), moderate to severe valvular disease or uncontrolled hypertension at screening.
4. Screening echocardiogram ejection fraction <55% or any other echocardiographic finding suggestive of clinically relevant cardiomyopathy.
5. Creatinine clearance of <60 mL/min (Cockcroft-Gault).
6. Positive test for HAV IgM, HBsAg, or HIV Ab.
7. Abnormal screening laboratory results that are considered clinically significant by the investigator.
8. History of clinical hepatic decompensation, e.g., variceal bleeding, spontaneous bacterial peritonitis, ascites, hepatic encephalopathy or active jaundice within the last year.
9. Any condition that, in the opinion of the investigator, would compromise the study's objectives or the well-being of the subject or prevent the subject from meeting the study requirements.

10. Participation in an investigational drug trial or having received an investigational vaccine within 30 days or 5 half-lives (whichever is longer) prior to study medication.
11. Clinically significant abnormal screening ECG findings (e.g., PR >200 msec, QRS interval >120 msec or corrected QT interval (QTc) >450 msec for male subjects and >470 msec for female subjects), based on an average of triplicate ECGs. Any evidence of heart block or bundle branch block is also exclusionary.
12. History or family history of abnormal ECG intervals, for example prolonged QT syndrome (*torsade de pointes*) or sudden cardiac death.

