NOTE: Laboratory abnormalities may have their grading defined in the DAIDs table below, however, all laboratory abnormalities do not necessarily represent an adverse event. If a laboratory abnormality is considered an AE, the AE need not have the same grade as the laboratory abnormality itself. The AE grade for a laboratory abnormality should be defined by the table above.

Major Clinical Conditions

Cardiovascular

PARAMETER	GRADE 1 MILD	GRADE 2 MODERATE	GRADE 3 SEVERE	GRADE 4 POTENTIALLY LIFE- THREATENING
Arrhythmia (by ECG or physical examination) Specify type, if applicable	No symptoms AND No intervention indicated	No symptoms AND Non-urgent intervention indicated	Non-life-threatening symptoms AND Non-urgent intervention indicated	Life-threatening arrhythmia OR Urgent intervention indicated
Blood Pressure Abnormalities¹ Hypertension (with the lowest reading taken after repeat testing during a visit) ≥ 18 years of age	140 to < 160 mmHg systolic OR 90 to < 100 mmHg diastolic	≥ 160 to < 180 mmHg systolic OR ≥ 100 to < 110 mmHg diastolic	≥ 180 mmHg systolic OR ≥ 110 mmHg diastolic	Life-threatening consequences in a participant not previously diagnosed with hypertension (e.g., malignant hypertension) OR Hospitalization indicated
< 18 years of age	> 120/80 mmHg	≥ 95 th to < 99 th percentile + 5 mmHg adjusted for age, height, and gender (systolic and/or diastolic)	≥ 99 th percentile + 5 mmHg adjusted for age, height, and gender (systolic and/or diastolic)	Life-threatening consequences in a participant not previously diagnosed with hypertension (e.g., malignant hypertension) OR Hospitalization indicated
Hypotension	No symptoms	Symptoms corrected with oral fluid replacement	Symptoms AND IV fluids indicated	Shock requiring use of vasopressors or mechanical assistance to maintain blood pressure
Cardiac Ischemia or Infarction Report only one.	NA	NA	New symptoms with ischemia (stable angina) OR New testing consistent with ischemia	Unstable angina OR Acute myocardial infarction

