- Direct microscopy: in case of abnormal urinalysis parameters (in listing only).

**Hormonology** parameters will be listed as follows: FSH (IU/L) and estradiol (pmol/L)

In case a laboratory test result is *censored* (no numeric value is available, but only a verbatim term), the following rules are applied:

- $< x$  or  $> x \rightarrow$  a numeric value will be imputed by a value exceeding the cut-off value with one unit.
- $\leq x$  or  $\geq x \rightarrow$  imputation by  $x$ .

Laboratory values will be graded based on the following toxicity grading scale: The Division of AIDS Table for Grading the Severity of Adult and Pediatric AEs (“DAIDS grading table”, version of November 2014), Appendix F - protocol version 8.0 of the 13rd of September 2016.

Lab values will also be graded based on WHO grading scale, but summary tables will be based on DAIDS grading scale only.

For haematology, blood chemistry, and coagulation, raw data and changes from baseline (Day 1) if applicable will be described by measurement time, for each cohort.

For all lab parameters with toxicity grade, a summary table with the number and percentage of subjects with treatment emergent grade 1-4 and 3+4 will be generated for each cohort for the worst post-baseline value. The same table will be provided by measurement time.

For haematology and blood chemistry, graphs of individual subject values (spaghetti plots) will be generated for each cohort for the following parameters: ALT, AST, alkaline phosphatase, total bilirubin, direct bilirubin, blood urea nitrogen, creatinine, CPK, BNP, haemoglobin, platelets and white blood cells.

A listing of all values of a parameter over time for any parameter with treatment emergent Grade 3 or 4 will be generated. A listing of all values of a parameter over time for any parameter with treatment emergent abnormal values will be also generated.

Values will be listed (raw data and change from baseline) and laboratory abnormal values will be flagged with their toxicity grades and clinical significance information.

For urinalysis, raw data will be described by measurement time, for each cohort.

Urinalysis values will be listed including direct microscopy if any.

Hormonology parameters will be listed only.

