### 8.3 Other safety parameters

#### 8.3.1 Vital signs data

Blood pressures (diastolic [DBP] and systolic [SBP]; mmHg), respiratory rate (breaths/min), body temperature (°C) and pulse rate (bpm) will be measured (see section [12.1](#)) for each cohort at the screening visit, Day 1, Week 1 and then once a week thereafter.

Raw data and changes from baseline (Day 1 pre-dose) will be described by measurement time, for each cohort.

A summary table with the number and percentage of subjects with PCSA values (defined in section [12.2](#)) will be generated by measurement time, for each cohort.

A specific listing of all values of a parameter over time for any parameter with PCSA values with clinical significance information will be generated.

Pulse rate, DBP, and SBP are classified in the following abnormality codes:

	Pulse (bpm)	DBP (mmHg)	SBP (mmHg)
Abnormally low	≤ 50	≤ 50	≤ 90
Abnormally high	≥ 120	-	-
Grade 1 or mild	-	> 90 - < 100	> 140 - < 160
Grade 2 or moderate	-	≥ 100 - < 110	≥ 160 - < 180
Grade 3 or severe	-	≥ 110	≥ 180

A summary table with the number and percentage of subjects with abnormal values (as defined above) will be generated for each cohort for the worst post-baseline value. The same table will be provided by measurement time.

A specific listing of all values of a parameter over time for any parameter with abnormal values with clinical significance information will be generated.

Values (raw data and changes from baseline) will be listed and PCSA and abnormal values will be flagged with clinical significance information.

Graph of mean (SE) by cohort over time will be plotted.

In determining the abnormalities, the following rules are applied:

- Worst grades/abnormalities are determined over the whole observational period, including post-baseline scheduled and unscheduled measurements.

- The abnormalities ‘abnormally low’ and ‘abnormally high’/grades are considered equally important, i.e. if a subject has an ‘abnormally low’ as well as an ‘abnormally high’ or graded post-baseline value, both abnormalities are shown in the tables. (This means that the sum of the percentages can be more than 100%.)

Definition treatment-emergent:

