An abnormality will be considered treatment-emergent if it is worse than the baseline. If the baseline is missing, the abnormality is always considered as treatment-emergent. A shift from ‘abnormally low’ at baseline to ‘abnormally high’ or ‘grade 1’ or ‘grade 2’ or ‘grade 3’ post baseline (or vice versa) is also treatment-emergent.

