Abnormalities on increase from baseline				
	-	[30; 60] ms	-	[30; 60] ms
	-	>60 ms	-	>60 ms

\* QTcB or QTcF

A summary table with the number and percentage of subjects with abnormal values (as defined above) will be generated for each cohort for the worst post-baseline value. The same table will be provided by measurement time.

A specific listing of all values of a parameter over time for any parameter with abnormal values with clinical significance information will be generated.

A specific listing of all overall interpretations over time for any subject with any overall interpretation considered to be clinically significantly abnormal will be created.

In determining the abnormalities, the following rules are applied:

- Worst abnormalities are determined over the whole observational period, including post-baseline scheduled and unscheduled measurements.
- The abnormalities 'abnormally low' and 'abnormally high' are considered equally important, i.e. if a subject has as well an abnormally low as an abnormally high post-baseline, both abnormalities are shown in the tables. (This means that the sum of the percentages can be more than 100%).

Cross-Tabulation of the worst ECG abnormalities in actual value versus the baseline value and Cross-Tabulation of the worst QTc increase versus the abnormality on the actual value will be presented.

Graphs of actual mean(SE), mean of change from baseline(SE) by cohort over time will be plotted. Spaghetti plots of PR for the patients who had prolonged PR interval or AV block (grade ≥ 1) will be plotted.

Definition treatment-emergent:

An abnormality will be considered treatment-emergent if it is worse than the baseline. If the baseline is missing, the abnormality is always considered as treatment-emergent. A shift from 'abnormally low' at baseline to 'abnormally high' or 'grade 1' or 'grade 2' or 'grade 3' post baseline (or vice versa) is also treatment-emergent.

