14.3.3.4.2	Number and percentage of subjects by treatment emergent toxicity grade (Grade 1,2,3,4,3+4) – Worst post-baseline value - Safety set
14.3.3.4.3	Number and percentage of subjects by treatment emergent toxicity grade (Grade 1,2,3,4,3+4) – By measurement time - Safety set
14.3.3.4.4	Listing of all values for subjects presenting any treatment emergent values that are grade 3 and 4 (toxicity grading scale) - Safety set
14.3.3.4.5	Listing of subjects with treatment emergent abnormal values - Safety set
14.3.4	Other safety parameters
14.3.4.1	Vital signs data
14.3.4.1.1	Vital signs parameters - Safety set
14.3.4.1.2	Number and percentage of subjects presenting PCSA values - Safety set
14.3.4.1.3	Listing of subjects presenting PCSA values - Safety set

14.3.4.1.4	Number and percentage of subjects presenting abnormal values – Worst post-baseline value - Safety set
14.3.4.1.5	Number and percentage of subjects presenting abnormal values – By measurement time - Safety set
14.3.4.1.6	Listing of subjects presenting abnormal values - Safety set
14.3.4.1.7	Plots of mean (SE) by cohort over time
14.3.4.2	Electrocardiogram data
14.3.4.2.1	ECG parameters – Safety set
14.3.4.2.2	Number and percentage of subjects with PCSA values - Safety set
14.3.4.2.3	Listing of subjects presenting PCSA values - Safety set
14.3.4.2.4	Listing of All ECG Parameters over time for Subjects with Any Post-baseline Overall Statement of Potentially Clinically Significant Abnormal ECG
14.3.4.2.5	Listing of Subjects with Potentially Progressive PR Prolongation
14.3.4.2.6	Number and percentage of subjects presenting abnormal values – Worst post-baseline value - Safety set
14.3.4.2.7	Number and percentage of subjects presenting abnormal values – By measurement time - Safety set
14.3.4.2.8	Listing of subjects presenting abnormal values - Safety set
14.3.4.2.9	Graphs of individual subject values (spaghetti plots) – Safety Set
14.3.4.2.10	Cross-Tabulation of the worst ECG abnormalities in actual value versus the baseline value
14.3.4.2.11	Cross-Tabulation of the worst QTc increase versus the abnormality on the actual value
14.3.4.2.12	Plots of actual mean(SE) by cohort over time
14.3.4.2.13	Plots of mean change from baseline(SE) by cohort over time
14.3.4.2.14	Spaghetti plot of PR for the patients who had prolonged PR interval

	or AV block (grade $\geq$ 1)
14.3.4.3	Echocardiogram data

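### SAP 8.3.1 defines a treatment-emergent vital-sign abnormality, but no vital-sign output uses it and no worst-versus-baseline table is planned, so no categorical table separates persistent from new findings

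*SAP*

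**What the plan says.** SAP 8.3.1 sorts pulse, diastolic and systolic pressure into abnormally low, abnormally high (pulse only) and Grades 1 to 3 (pressures only). It plans a table of the "number and percentage of subjects with abnormal values (as defined above) will be generated for each cohort for the worst post-baseline value", and the same table by measurement time. In the SAP's list of outputs (Appendix 3) these are 14.3.4.1.4 and 14.3.4.1.5, titled "Number and percentage of subjects presenting abnormal values". The section ends with a definition: "An abnormality will be considered treatment-emergent if it is worse than the baseline".

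The laboratory section (SAP 8.2) carries a similar definition and uses it: the "number and percentage of subjects with treatment emergent grade 1-4 and 3+4 will be generated for each cohort". The laboratory table titles in Appendix 3 repeat the restriction, and a cross-tabulation of worst grade against baseline is planned. For ECG, SAP 8.3.2 plans a "Cross-Tabulation of the worst ECG abnormalities in actual value versus the baseline value". Vital signs have no such table.

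On blood-pressure limits, SAP 8.3.1 starts Grade 1 above 140 mmHg systolic and above 90 mmHg diastolic, and the potentially clinically significant abnormality (PCSA) limits in SAP Appendix 2 do the same. Protocol Appendix F starts Grade 1 at "140 to < 160 mmHg systolic", with a diastolic range that likewise includes 90.

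**The concern.** Protocol 3.2.1 names vital signs in the primary endpoint, and the synopsis gives no comparator. For a categorical finding, the subject's own baseline is then the main reference for deciding whether anything changed. A programmer who follows the text and table titles will count every abnormal post-baseline value, including one unchanged since Day 1.

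Such subjects can enter. Protocol 4.3 excludes uncontrolled hypertension and clinically significant cardiovascular illness, and Table 5-2 prohibits beta-blockers. No numeric limit is set for blood pressure, and none for resting heart rate. A subject with a pulse of 50 or a systolic pressure of 145 on Day 1 is therefore not excluded by any stated limit.

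The categories matter here. Protocol 1.3.1 reports lower heart rate in dogs given odalasvir and, in preliminary data from a further dog study, lower systolic and diastolic pressure. Low pulse and low pressure are rows of this table. With 10 to 20 subjects per cohort, one subject moves a percentage by 5 to 10 points.

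**Working it through.** **1. Which outputs use baseline categorically**

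| Data | Counts restricted to treatment-emergent | Worst value against baseline | Increase-from-baseline categories |
|---|---|---|---|
| Laboratory (8.2) | Yes, in text and titles | Yes | Not needed |
| ECG (8.3.2) | No | Yes (14.3.4.2.10, 14.3.4.2.11) | Yes, for PR and QTc |
| Vital signs (8.3.1) | No | No | No |

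The gap is specific to vital signs.

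**2. Effect on the count, under assumed rates.** The documents give no baseline prevalence, so these are illustrations. Let n = 20, b = share with an abnormality present at baseline and unchanged, t = share of the rest with a new one, t = 5%.

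- Any abnormal value: n × [b + (1 − b)t]. Treatment-emergent only: n × (1 − b)t.
- b = 5%: 20 × (0.05 + 0.95 × 0.05) = 1.95, against 20 × 0.95 × 0.05 = 0.95.
- b = 10%: 20 × (0.10 + 0.90 × 0.05) = 2.90, against 0.90.
- b = 20%: 20 × (0.20 + 0.80 × 0.05) = 4.80, against 0.80.

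**3. Simulation with no drug effect.** Integer readings, 400,000 subjects per scenario, one baseline reading and nine post-baseline readings (eight weekly visits plus the safety follow-up of an 8-week cohort). Only the high-pressure grades were simulated. All means and standard deviations (SDs) are assumptions.

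- Systolic: mean 120 to 130, between-subject SD 11 to 12, within-subject SD 7 to 8. The table flags about 19 to 54% of subjects; about 21 to 33% of those flagged are no worse than their own baseline category.
- Diastolic: mean 75 to 80, SDs 7 to 8 and 5 to 6. About 13 to 22% of those flagged are no worse than baseline.

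**4. The 140/90 limits.** Grading every integer reading under both schemes (high side, Grades 1 to 3), the SAP and Appendix F disagree only at systolic 140 and diastolic 90. The PCSA limits use the same strict inequality, so those two readings are abnormal in no SAP table. A subject drops out of the worst-value table only if the highest reading is exactly 140 (or 90). Under the assumptions in step 3:

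- Systolic: about 2.3 to 3.4% of subjects; 20 × 0.023 = 0.5 to 20 × 0.034 = 0.7 per cohort of 20.
- Diastolic: about 3 to 5%; 20 × 0.03 = 0.6 to 20 × 0.05 = 1.0 per cohort of 20.

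**5. The ECG definition.** It treats a shift from abnormally low to abnormally high, or to Grade 1, 2 or 3, as treatment-emergent. The ECG categories in 8.3.2 are low, high, borderline, prolonged and pathologically prolonged, plus increases from baseline. None is a grade, so that part cannot be programmed as written.

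**The case against.** **The restriction may be intended.** The definition closes 8.3.1 just as a similar one closes 8.2, so the authors may have meant it to govern the tables. That cannot be excluded. But 8.2 states the restriction in its text and titles and 8.3.1 does not. If it is intended, it still has to be written down.

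**Baseline is not ignored for vital signs.** The SAP plans change-from-baseline summaries, abnormality counts by visit, and listings of all values and changes with abnormal ones flagged. In cohorts of 10 to 20 a careful reader can find a persistent abnormality in the listings. This stands, and it limits the point to the categorical tables.

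**A reader might infer that the ECG tables have the same defect.** The documents do not support that. Protocol 4.3 excludes PR above 200 ms, QRS above 120 ms and "corrected QT interval (QTc) >450 msec for male subjects and >470 msec for female subjects". Women with a QTc just above 450 ms can enter and fall in the SAP's borderline category without any change, and low heart rate and short PR have no numeric entry limit. The planned ECG cross-tabulations, the categories of PR and QTc increase and the listing of PR change above 20 ms deal with most of this. Only the stray grade wording needs correcting.

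**A reader might infer that the SAP presents old findings as drug effects.** It does not. The tables are labelled post-baseline, and "Worst grades/abnormalities are determined over the whole observational period", which includes follow-up. No attribution is claimed.

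**The SAP never says that its blood-pressure codes follow Appendix F.** It adds numeric low limits, has no Grade 4 and does not adopt the Appendix F rule on repeat readings. So a reader cannot say that the SAP breaks a scale it adopted. Still, Grades 2 and 3 agree exactly, and an unexplained difference at Grade 1 alone looks like a slip.

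**Conclusion.** The point holds for vital signs. A treatment-emergent definition is given and left unused, and no planned categorical table separates persistent from new or worsened pulse and blood-pressure abnormalities. It should be corrected before database lock. It changes no data collection and no inference, since the SAP does no significance testing.

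The size cannot be fixed from the documents. Under the assumed distributions, about a fifth to a third of subjects flagged for high systolic pressure would be no worse than at baseline, and somewhat fewer for diastolic. The restriction would not turn the table into a measure of drug effect: in the same no-effect simulation about 67 to 79% of those flagged for systolic pressure (100% minus 33% and 21%) still count as treatment-emergent, because nine readings are compared with one.

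The 140/90 mismatch is minor, at roughly 2 to 5% of subjects or about 0.5 to 1 per cohort of 20. Readings at the limit form a larger share of all readings that Appendix F would grade (9 to 14% systolic and 14 to 22% diastolic under similar assumptions), but the worst-value table counts subjects, so those shares overstate the loss.

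**What to change.** 1. In SAP 8.3.1 and Appendix 3, state that tables 14.3.4.1.4 and 14.3.4.1.5 count treatment-emergent abnormalities, meaning worse than the baseline category, as the laboratory tables do. Instead, or in addition, add a cross-tabulation of worst post-baseline category against baseline category for pulse, systolic and diastolic pressure. The cross-tabulation shows both the persistent and the new findings.
2. Make the Grade 1 limits in 8.3.1 and the upper PCSA limits in Appendix 2 inclusive (≥140 and ≥90 mmHg), or state why they differ from protocol Appendix F.
3. In the ECG treatment-emergent definition (8.3.2), replace the grade wording with the ECG categories. The ECG tables need no other change.

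The cost is SAP wording, minor reprogramming and at most one new table. Counts of mild blood-pressure findings will rise slightly from item 2.

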### 8.3.2 Electrocardiogram data

Standard 12-lead ECG parameters (including heart rate (bpm), PR interval (ms), QRS duration (ms), QT interval (ms), Bazett QTc interval (QTcB; ms) and Fridericia QTc interval (QTcF; ms)) from both automatic and centrally read data, information on T- (normal or abnormal) and U-waves (normal or abnormal) and ECG abnormality will be measured (see section [12.1](#)) for each cohort at the screening visit, Day 1, Week 1 and then once a week thereafter.

The mean of the triplicate ECGs will serve as analysable data for each visit. If one or more assessment is missing/not done then the mean will be calculated using the available assessments.

Centrally read data will be used for summary statistics and both locally and centrally read data will be listed.

Raw data and changes from baseline (Day 1 pre-dose) (except for T-and U-wave and ECG abnormality) will be described by measurement time, for each cohort.

A summary table with the number and percentage of subjects with PCSA values (defined in section [12.2](#)) will be generated by measurement time, for each cohort.

Graphs of individual subject values (spaghetti plots) will be generated for each cohort for the following parameters: PR, QRS, QTcB, and QTcF. These graphs will include indications for the most conservative upper and lower limit of normal.

A specific listing of all values of a parameter over time for any parameter with PCSA values with clinical significance information will be generated.

A listing of all values over time for subjects with any clinically significantly abnormal ECGs will also be generated.

A listing of subjects with potentially progressive PR prolongation will be generated.

Potentially progressive PR prolongation is defined as any subject who has a post-baseline change of >20 ms from the highest pre-dose value.

Values (raw data/T- and U-wave/ECG abnormalities and changes from baseline) will be listed and data out of PCSA range will be flagged with clinical significance information.

The following abnormality categories are defined:

Abnormality Code	ECG parameter			
	HR	PR	QRS	QT corrected *
Abnormalities on actual values				
Abnormally low	≤50 bpm	<120 ms	NA	-
Abnormally high	≥120 bpm	]200-240] ms ]240-300] ms >300 ms	>120 ms	-
Borderline: ]450 ms, 480 ms]	-	-	-	450 ms < QT c ≤ 480 ms
Prolonged: ]480 ms, 500 ms]	-	-	-	480 ms < QT c ≤ 500 ms
Pathologically prolonged: >500 ms	-	-	-	QT c > 500 ms
Abnormalities on increase from baseline				
	-	[30; 60] ms	-	[30; 60] ms
	-	>60 ms	-	>60 ms

\* QTcB or QTcF

A summary table with the number and percentage of subjects with abnormal values (as defined above) will be generated for each cohort for the worst post-baseline value. The same table will be provided by measurement time.

A specific listing of all values of a parameter over time for any parameter with abnormal values with clinical significance information will be generated.

A specific listing of all overall interpretations over time for any subject with any overall interpretation considered to be clinically significantly abnormal will be created.

In determining the abnormalities, the following rules are applied:

- Worst abnormalities are determined over the whole observational period, including post-baseline scheduled and unscheduled measurements.
- The abnormalities 'abnormally low' and 'abnormally high' are considered equally important, i.e. if a subject has as well an abnormally low as an abnormally high post-baseline, both abnormalities are shown in the tables. (This means that the sum of the percentages can be more than 100%).

Cross-Tabulation of the worst ECG abnormalities in actual value versus the baseline value and Cross-Tabulation of the worst QTc increase versus the abnormality on the actual value will be presented.

Graphs of actual mean(SE), mean of change from baseline(SE) by cohort over time will be plotted. Spaghetti plots of PR for the patients who had prolonged PR interval or AV block (grade ≥ 1) will be plotted.

Definition treatment-emergent:

An abnormality will be considered treatment-emergent if it is worse than the baseline. If the baseline is missing, the abnormality is always considered as treatment-emergent. A shift from 'abnormally low' at baseline to 'abnormally high' or 'grade 1' or 'grade 2' or 'grade 3' post baseline (or vice versa) is also treatment-emergent.

